| Efficacy Endpoints | 
 1. Improvement in skin appearance comparing pre and at 1 month (except site #3), 3 months and 6 months post last treatment photographs (as assessed by blinded investigators): 
 • Success is defined by correct identification of the pre and post treatment photos of patients completed the treatment at 1 month (except site #3), 3 months and 6 months post treatment. • At least 2 out of 3 blinded evaluators should agree on the assessment. 2. 3D Photographic analysis will be conducted at 1 month (except site #3), 3 months and 6 months follow up visits and compared to the baseline. 3. Investigator assessment of the skin appearance improvement comparing pre and post treatment using 0 - 4 -points Likert scale at 1 month (except site #3), 3 months and 6 months follow up visits: 
 • 4 = Significantly marked improvement; 3 = Marked improvement; 2 = Moderate improvement; 1 = Slight improvement; 0 = No difference 4. Improvement assessment will be performed independently by the subject himself 4 points Likert scale questionnaire (Global Aesthetic Improvement Scale), as follows: 
 • 4 = Significantly marked improvement; 3 = Marked improvement; 2 = Moderate improvement; 1 = Slight improvement; 0 = No difference. 5. Subject assessment of satisfaction will be filled out by subjects using a 5-points Likert scale, as follows: 
 • +2 = Very satisfied; +1 = Satisfied; 0 = Indifferent; -1 = Disappointed; -2 = Very disappointed. 6. Optional: Positive changes in histologic evaluation: up to 5 subjects will undergo biopsies of the treated area for histology at baseline and at 3M follow-up visit. Histological sections will be stained using elastin, H&E and other collagen specific stains. (except site #3) |

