6.1 Efficacy Endpoints

1. Improvement in in skin laxity comparing pre and at 1 month (except site #3), 3 months and 6 months post last treatment photographs (as assessed by blinded investigators):
 - Success is defined by correct identification of the pre and post treatment photos of patients completed the treatment at 1 month (except site #3), 3 months and 6 months post treatment.
 - At least 2 out of 3 blinded evaluators should agree on the assessment.
2. 3D Photographic analysis will be conducted at 1 month (except site #3), 3 months and 6 months follow up visits and compared to the baseline.
3. Investigator assessment of the skin appearance improvement comparing pre and post treatment using 0 - 4 -points Likert scale at 3 months and 6 months follow up visits:
 - 4 = Significantly marked improvement; 3 = Marked improvement; 2 = Moderate improvement; 1 = Slight improvement; 0 = No difference
4. Improvement assessment will be performed independently by the subject himself 4 points Likert scale questionnaire (Global Aesthetic Improvement Scale), as follows:
 - 4 = Significantly marked improvement; 3 = Marked improvement; 2 = Moderate improvement; 1 = Slight improvement; 0 = No difference.
5. Subject assessment of satisfaction will be filled out by subjects using a 5-points Likert scale, as follows:
 - +2 = Very satisfied; +1 = Satisfied; 0 = Indifferent; -1 = Disappointed; -2 = Very disappointed.
6. Optional: Positive changes in histologic evaluation: up to 5 subjects will undergo biopsies of the treated area for histology at baseline and at 3M follow-up visit. Histological sections will be stained using elastin, H&E and other collagen specific stains.

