8.1 Screening and Baseline (Visit 1)

Screening visit will be performed in order to determine subject eligibility and to collect all required demographic and baseline clinical information. Study procedures and available treatment options, including the RF technology will be described in detail to the subject. Subject will be assured that the decision regarding participation in the study is strictly voluntary and that they are free to change their mind at any stage.

The subject will review the informed consent form and the study will be explained to the subject including all risks, potential benefits, procedures, visit requirements, and other alternative treatment options. If the subject qualifies and wishes to participate, he/she will complete the ICF with a signature and date. The original will be retained with subject's records and a copy will be provided to the subject. Subjects will then be screened for study eligibility according to inclusion and exclusion criteria.

The following Demographic and Baseline Measurements will be performed:

- Demographic data including gender, age, race, skin type (Fitzpatrick scale).
- ICF - Prior to any study procedures, informed consent will be obtained. When the subject fully understands the possible benefits and risks of the study, the subject will be asked to sign and date the informed consent form (ICF). The subject will be given a copy of the signed ICF.
- Subject ID - subjects will be assigned a study subject ID number.
- Medical History - A medical history will be obtained to determine if the subject meets the study criteria, including a list of all prescribed and over the counter medications taken within the previous 6 months will be recorded.
- Pregnancy Screen - Subjects who are capable of becoming pregnant will undergo a urine pregnancy test. This will be repeated prior to all treatments, and at the end of the study (last FU visit, 6-month FU).
- If the Screening and Treatment procedures are not conducted on the same day, the urine pregnancy test will be repeated on the first treatment day.
- Photography – Baseline photographs will be obtained using a consistent camera and subject placement settings with a digital imaging system.
- 3D Photography – Baseline 3D pictures will be obtained using 3D system. PI will ensure the same camera is used throughout the study.
- Up to 5 study participants be selected for baseline biopsy

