8.3 Follow up visits (Visits 4, 5 and 6)

Follow up visits will be conducted at 4 weeks (1-month FU) (except site #3), 12 weeks (3M FU) and 24 weeks (6M FU) following last treatment.

The 1 month (except site #3), **3 months and 6 months follow up visits** will include the following assessments:

- Standardized medical photography
- 3D Photography

| | | |
|--------------------------------------------------------------------------------------------------------|------------------------------------------------------------------------|-----------------------|
|  I N M O D E | Treatment with the Evoke System for Facial and Submental Laxity | |
| | Protocol No: DO609886A SIRB ID: | Rev. Date: 29 Oct. 20 |

- Urine Pregnancy Test (only last 6 months FU visit)
- Investigator assessment of the skin appearance improvement comparing pre and post treatment using 4-point Likert scale
- Subject’s Improvement and Satisfaction questionnaires
- Post final treatment biopsy will be performed (up to 5 subjects)
- AE evaluation recording
- Concomitant medication recording

9. Adverse Events Reporting

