11.1 Case Report Forms (CRFs)

Paper case report forms will be used in this trial. All protocol-required information collected during the study must be entered in the appropriate field of the case report form (CRF). The investigator, or designated representative, should complete the appropriate CRF fields as soon as possible after information is collected. The information must match the information that exists as source documents in

| | | |
|---------------------------------------------------------------------------------|-----------------------------------------------------------------|-----------------------|
|  | Treatment with the Evoke System for Facial and Submental Laxity | |
| | Protocol No: DO609886A SIRB ID: | Rev. Date: 29 Oct. 20 |

the clinic chart, hospital chart, and/or investigator's files. An explanation should be given for all missing data.

It is the investigator's responsibility to assure the accurate completion, review, and approval of all CRFs and the timely completion and submission of all adverse event forms.

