14.1 Analysis Sets

- Safety Analysis Set

The safety analysis set will include all subjects using Embrace procedures at least a single time.

- Performance Analysis Set

Performance analysis set will consist of all subjects providing at least one post treatment performance measurement.

- Treatment of Missing Values

Only observed data will be used; i.e. missing data will not be imputed.

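### Both 0–4 improvement scales lack a level for worsening, so their means cannot fall below zero, and section 14.2 does not rule out testing them against that floor

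*Combined protocol and SAP*

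**What the plan says.** Section 6.1 items 3 and 4, and the same items in the synopsis, give both improvement ratings one set of levels: "4 = Significantly marked improvement; 3 = Marked improvement; 2 = Moderate improvement; 1 = Slight improvement; 0 = No difference". The subject's rating is introduced as follows: "Improvement assessment will be performed independently by the subject himself 4 points Likert scale questionnaire (Global Aesthetic Improvement Scale". Section 5 places both ratings under the secondary objectives. Item 5 of the same list, satisfaction, has negative levels (its top level is signed plus): "2 = Very satisfied; +1 = Satisfied; 0 = Indifferent; -1 = Disappointed; -2 = Very disappointed".

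The ratings are collected only at follow-up. Section 8.3 lists "Investigator assessment of the skin appearance improvement comparing pre and post treatment using 4-point Likert scale" and the subject questionnaires. The baseline list in section 8.1 has photographs and 3D images ("Baseline 3D pictures will be obtained using 3D system") but neither rating.

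On missing values, section 11.1 says "An explanation should be given for all missing data" and section 14.1 says "Only observed data will be used; i.e. missing data will not be imputed". Section 14.2 calls for means and standard deviations and for a paired t-test of before and follow-up scores at two-sided 0.05. It does not name the endpoints that the test covers.

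**The concern.** Section 9.2 anticipates visible harm in the treated area, including pigment change and scarring, so worsening is a foreseen outcome. On these two scales it has nowhere to go. A worsened subject takes the same score as an unchanged one, or the item is left blank, explained and dropped. Either way the rating does not show the worsening and the mean cannot be negative.

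The analysis section adds to this. The only named test needs a before score, and these ratings have none. If it is applied anyway, the only evident before value is 0. That is the lowest possible score, so the nominally two-sided test can reject in one direction only. A small positive mean, or a p-value against 0, could then be reported as improvement when the net change is nil or negative.

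**Working it through.** The plan gives no SD, worsening rate, effect size or pooled sample size, so there is no stated figure to reproduce. Sizes used: n = 75 (five sites of about 15, synopsis), n = 60 (four sites, since site #3 has no 1-month visit) and n = 15 (one site). Alpha is two-sided 0.05 (section 14.2).

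**Step 1: fixed examples, no noise model.** If k of n subjects score 1 and the rest score 0, the mean is k/n, the variance is k(n−k)/[n(n−1)], and the one-sample statistic against 0 is t = √[k(n−1)/(n−k)] on n−1 df.

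- *Balanced case.* Five subjects one level better, five one level worse, the rest unchanged. On a two-directional scale the mean is 0 and p = 1.0.
  - Worsened scored 0 (k = 5): n = 75, t = √(5×74/70) = 2.30, p = 0.024; n = 60, t = √(5×59/55) = 2.32, p = 0.024; n = 15, t = √(5×14/10) = 2.65, p = 0.019.
  - Worsened left blank (n falls by 5): n = 70, p = 0.024; n = 55, p = 0.024; n = 10, t = √(5×9/5) = 3.00, p = 0.015.
- *Sign reversal at n = 75.* 8 better, 38 worse, 29 unchanged.
  - Two-directional: mean (8−38)/75 = −0.40, SD 0.678, t = −5.11, p < 0.0001.
  - Worsened scored 0: mean 8/75 = +0.11, t = √(8×74/67) = 2.97, p = 0.004.
  - Worsened left blank: mean 8/37 = +0.22, t = √(8×36/29) = 3.15, p = 0.003.
- *Smallest count that is significant.* Four ratings of slight improvement, all others 0, give p = 0.045 at n = 75 (mean 4/75 = 0.053), 0.045 at n = 60 and 0.041 at n = 15.

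**Step 2: equal shares q better and worse by one level (no net change).** From step 1, the floored test rejects when at least four subjects score 1, so the rejection probability is P[Binomial(n, q) ≥ 4]:

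- n = 75: 52% at q = 0.05, 95% at q = 0.10
- n = 60: 35% and 86%
- n = 15: 0.5% and 5.6%, then 35% at q = 0.20 and 70% at q = 0.30

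**Step 3: no true effect, symmetric rating noise.** Score = a Normal(0, SD) value rounded and clipped to [floor, 4]; 40,000 simulated trials per setting. Rejection rate against 0:

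| Floor | n | SD 0.25 | 0.3 | 0.4 | 0.5 | 0.75 | 1.0 |
|---|---|---|---|---|---|---|---|
| 0 (as planned) | 75 | 9% | 48% | 96% | >99% | 100% | 100% |
| 0 | 60 | 5% | 32% | 89% | 99% | 100% | 100% |
| 0 | 15 | <1% | <1% | 7% | 20% | 47% | 60% |
| −1 | 75 | 4% | 5% | 5% | 5% | 5% | 9% |
| −2 | 75 | 4% | 5% | 5% | 5% | 5% | 5% |

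At n = 60 a floor of −1 gives 8% at SD 1.0. A floor of −2 stays at about 5% or less at all three sizes.

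**Step 4: effect on the reported mean**, floor 0 against floor −2, for SD 0.5 / 0.75 / 1.0:

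- true mean 0: +0.160 / +0.275 / +0.375
- true mean 1: +0.001 / +0.023 / +0.073
- true mean 2: 0.000 / 0.000 / +0.006

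**The case against.** The strongest reply is that the test is hypothetical. Section 14.2 pairs before and follow-up scores, and these ratings already compare pre with post and have no before score. On a plain reading the t-test does not reach them. That is fair: the plan does not assign the test to these ratings. But it then gives them no inferential analysis at all, and the means it does call for are shifted by the floor whether or not a test is run.

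Second, worsening can show elsewhere. Pigment change and scarring would be recorded as adverse events. The 3D comparison and satisfaction on −2 to +2 can move either way. In the blinded photograph comparison ("At least 2 out of 3 blinded evaluators should agree on the assessment"), a worsened pair put in the wrong order is not a success. This stands and limits the harm, but none of it corrects the mean of the two ratings.

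Third, the inputs are assumed. The noise model implies a share rated worse of Φ(−0.5/SD): about 2% at SD 0.25, 16% at 0.5, 25% at 0.75 and 31% at 1.0. The rejection rates near 100% depend on such shares, and the sign-reversal case has 38 of 75 (51%) worse, which nothing in the plan suggests. If 5% worsen by one level and are scored 0, the mean rises by only 0.05. This stands as a limit on size; the missing level itself depends on no assumption.

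Fourth, section 6.1 item 3 schedules the investigator rating at 3 and 6 months only, while the synopsis and section 5 add 1 month. The n = 60 case is therefore secure only if the 1-month rating is made. The results at 75 and 15 do not depend on it.

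**Conclusion.** The concern holds. Neither improvement scale can record worsening, and section 14.2 leaves open a test against the scale floor. That the mean cannot be negative, and that such a test can reject only towards improvement, follows from the levels alone.

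The size depends on assumptions. The distortion matters when the true mean is near 0 and subjects are pooled. It is negligible when the true mean is about 2, or at a single site with little rating noise (rejection 7% or less up to SD 0.4). SD, shares worsening and pooled n are all assumed, because the plan gives none. Since these are secondary endpoints and other measures may reveal worsening, this is a change that should be made, but it does not undermine the study as a whole.

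**What to change.** 1. Add to section 14.2:

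> Ratings on the 0–4 improvement scales will not be tested against 0. The full distribution and the proportion rated 2 or more, with exact 95% CI, will be reported at each visit, with the number of blank ratings and the reason.

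The cut at 2 is a choice: under the step 3 model, noise alone reaches 2 in 0.1% of ratings at SD 0.5, 2.3% at 0.75 and 6.7% at 1.0. If slight improvement is considered relevant, the full distribution still shows it. The cost is a wording change through an IRB-approved amendment (section 10.3) and the loss of a p-value on two secondary endpoints. Precision will be modest: 38 of 75 has an exact 95% CI of 39–62%, and 8 of 15 has 27–79%.

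2. Where forms can still be revised, add at least two worsening levels to both (for example −1 slight and −2 moderate worsening) and report the proportion below 0 with exact 95% CI. A single −1 level holds the error rate up to SD 0.75 but gives 8–9% at SD 1.0 with n = 60 to 75. This means revising paper CRFs at up to five sites. Ratings already made on the 0–4 form cannot be pooled with the new ones and must be reported separately. With no subject rated worse, the upper 95% limit is 4.8% at n = 75 and 22% at n = 15.

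Neither change removes open-label expectation bias.

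Separately, and adding no weight to this point, reconcile the satisfaction scale: the secondary objectives (synopsis and section 5) put it on 0–4, while the endpoint lists (synopsis and section 6.1) run from −2 to +2. On 0–4, the one two-directional rating would lose its negative side as well.

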6.2 Safety Endpoint

- Observation, assessment and recording of adverse events.
- Discomfort Level assessment - subject will be asked to rate discomfort during the procedure. Discomfort will be assessed based on the Numerical Scale Response (NSR). The subject will be presented a scale and asked to make a mark along the scale. The subject will be asked to rate discomfort from 0 to 10, with 0 equaling no discomfort and 10 equaling the worst possible discomfort. A number is obtained by measuring up to the point the subject has indicated. **(Appendix 3 – Discomfort Assessment)**
- Evaluations will be done immediately after treatments and at all follow-up visit. The frequency, severity and causality of all adverse events will be recorded.

| | | |
|---------------------------------------------------------------------------------|-----------------------------------------------------------------|-----------------------|
|  | Treatment with the Evoke System for Facial and Submental Laxity | |
| | Protocol No: DO609886A SIRB ID: | Rev. Date: 29 Oct. 20 |

- Number, severity and type of any adverse event recorded throughout the course of the study.

7. Study Population

7.1 General Considerations

The study will recruit approximately 15 subjects per site, between the ages of 35-75, healthy adults with visible signs of aging, seeking skin laxity treatments.

Treatment areas include face, under chin

Eligible subjects will be screened. Investigators will screen subjects based on the inclusion/exclusion criteria described below after a written informed consent is signed.

7.2 Subject Withdrawal and Replacement

Subjects enrolled in the study can discontinue their participation at any time for any reason without prejudice or reduction in the quality of their medical care. The investigators or sponsor can terminate a subject's participation in this study to protect the subject's health or if the subject fails to follow directions resulting in noncompliance to study procedures. Subjects who withdraw or are terminated from the study may be replaced to ensure approximately 15 subjects (per site) have completed the study. Subjects who fail to complete the treatment will be replaced and will not be evaluable.

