| Study Duration | Study duration for each subject is approximately 10 months (including screening, three treatments once in 2 weeks and 3 follow-up visits at 1m (except site #3), 3 months and 6 months post last treatment. Overall study duration will be approximately 14 months, depending on the subject recruitment rate. |
| Study Objectives | The aim of the study is to evaluate the efficacy, patient comfort, and patient satisfaction after Evoke treatment for face and submental area |
| Primary Objective | 
 1. Evaluate improvement in skin appearance comparing pre and at 1 month (except site #3), 3 months and 6 months post last treatment photographs (as assessed by blinded investigators) 2. Evaluate Improvement in skin appearance using 3D Photographic analysis at 1month (except site #3), 3 months and 6 months follow up visits and compared to the baseline. |
| Secondary Objectives | 
 1. Evaluate Investigator assessment of the skin appearance improvement comparing pre and post treatment using 0 - 4 -points Likert scale at 1month (except site #3), 3 months and 6 months follow up visits. 2. Evaluate Subject assessment of improvement and satisfaction using 0 - 4 -points Likert scale at 1month (except site #3), 3 months and 6 months follow up visits. |

| | | |
|--------------------------------------------------------------------------------------------------------|------------------------------------------------------------------------|-----------------------|
|  I N M O D E | Treatment with the Evoke System for Facial and Submental Laxity | |
| | Protocol No: DO609886A SIRB ID: | Rev. Date: 29 Oct. 20 |

| | |

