The aim of the study is to evaluate the efficacy, patient comfort and patient satisfaction after Evoke treatment.

Primary Objective:

1. Evaluate improvement in skin appearance comparing pre and at 1 month (except site #3), 3 months and 6 months post last treatment photographs (as assessed by blinded investigators)
2. Evaluate Improvement in skin appearance using 3D Photographic analysis at 1 month (except site #3), 3 months and 6 months follow up visits and compared to the baseline.

Secondary Objective:

1. Evaluate Investigator assessment of the skin appearance improvement comparing pre and post treatment using 0 - 4 -points Likert scale at 1 month (except site #3), 3 months and 6 months follow up visits.

| | | |
|--------------------------------------------------------------------------------------------------------|------------------------------------------------------------------------|-----------------------|
|  I N M O D E | Treatment with the Evoke System for Facial and Submental Laxity | |
| | Protocol No: DO609886A SIRB ID: | Rev. Date: 29 Oct. 20 |

2. Evaluate Subject assessment of improvement and satisfaction using 0 - 4 -points Likert scale at 1 month (except site #3), 3 months and 6 months follow up visits.
3. Optional: Evaluate histological changes to treatment area skin taken at 3M FU versus baseline. (except site #3)

6. Study Endpoints

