 - Secure the Applicator with 2 additional adjustable straps. One strap is positioned on the back of the head, and one across the top or the head.
- For Chin Applicator:
 - Place the Applicator on the under-chin area. Ensure that the electrodes are positioned on the soft tissue, not on bony areas. The position of the applicator should not be angled or tilted.
 - Secure the Applicator with the adjustable strap on the top of the head. Use additional silicone strap to secure the Applicator on the chin to prevent it from sliding to the neck.
 - There should be a complete coupling between all Applicator electrodes and the skin during the treatment session.
 - Adjust or reposition the Applicator if one or more electrodes do not have complete contact with the skin. In the event that the proper coupling between the electrodes and the skin cannot be achieved, due to patient anatomy or surface irregularities (such as

| | | |
|--------------------------------------------------------------------------------------------------------|------------------------------------------------------------------------|-----------------------|
|  I N M O D E | Treatment with the Evoke System for Facial and Submental Laxity | |
| | Protocol No: DO609886A SIRB ID: | Rev. Date: 29 Oct. 20 |

moles, scars, etc.), disable the specific electrode. Treatments can still be conducted if one or more of the electrodes are disabled.

- Provide patient with Patient Call Button and educate on proper use.
- Start with lower energy levels and gradually increase according to patient's comfort level. Set treatment time to desired treatment duration and press the Start button.
- Treatments can be paused by pressing the Pause button in the upper left corner of the screen.
- In case the Applicator needs to be readjusted or repositioned, pause the treatment, readjust the Applicator and restart the treatment. DO NOT readjust the Applicator when treatment is activated.
- The procedure should NOT feel hot or intolerable to the patient. If the patient complains of discomfort, immediately pause the treatment and inspect the area. Treatment can be continued with one or more of units disabled. Reduce RF power if required.
- Consequent cyclic electrodes activation during the procedure will be reflected on the screen.

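### Section 7.2 makes treatment non-completers non-evaluable, while the section 14.1 analysis sets keep them; as worded, 7.2 could remove early stoppers and flatter the results

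*Combined protocol and SAP*

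**What the plan says.** Section 7.2 of the combined protocol and SAP first allows replacement of withdrawn or terminated subjects, so that about 15 per site complete. It then adds a separate rule about treatment: "Subjects who fail to complete the treatment will be replaced and will not be evaluable". That sentence is not limited to efficacy or to any endpoint.

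Section 14.1 defines two sets, and neither mentions completion:

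- Safety: "The safety analysis set will include all subjects using Embrace procedures at least a single time". Embrace is an evident slip for Evoke.
- Performance: "Performance analysis set will consist of all subjects providing at least one post treatment performance measurement".

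Section 14.1 also says that observed data only are used, without imputation.

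Three other places bear on the point:

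- **Photo identification.** Section 6.1, endpoint 1, carries its own restriction: "Success is defined by correct identification of the pre and post treatment photos of patients completed the treatment". Endpoints 2 to 5 (3D analysis, investigator rating, subject improvement, subject satisfaction) carry none.
- **Discomfort.** Section 6.2 lists it as a safety endpoint: "subject will be asked to rate discomfort during the procedure". Comfort is also a study aim in section 5: "The aim of the study is to evaluate the efficacy, patient comfort and patient satisfaction after Evoke treatment".
- **Length of the course.** The synopsis (Study Duration) describes "three treatments once in 2 weeks", whereas section 8.2 allows up to three. Completion is not defined.

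**The concern.** A subject who stops after the first or second session is in the analysis under 14.1 and out of it under 7.2. The plan gives no order of precedence, so the population could be chosen after results are seen.

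Stopping need not be unrelated to outcome. Section 7.2 lets subjects leave for any reason and lets the investigator or sponsor stop a subject on health grounds. Subjects who found treatment uncomfortable or disappointing are plausible stoppers. Replacing them restores the count of about 15 per site, so the reported number of completers would not show the loss. The study is open label and describes no control arm, so no comparison group would offset a shift.

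Comfort and satisfaction are stated aims, and the 3D analysis serves a primary objective. Those are the results that 7.2, applied as worded, could make look better than they are.

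**Working it through.** The plan states no stopping rate, expected score or sample-size derivation, so there is no planned figure to reproduce. The check has two parts.

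**1. Where the rules disagree.** Take a subject who stops early, assuming that a full course is three sessions.

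| Result | Under 14.1 | Under 7.2 as worded | Comment |
|---|---|---|---|
| Adverse events, discomfort | In (safety set) | Out, if 7.2 is read without limit | Data exist, because both are assessed at treatment sessions (6.2, 8.2) |
| Endpoint 1, photo identification | In the set if measured | Out | Already restricted to completers by 6.1 |
| Endpoints 2 to 5, subject returns | In (performance set) | Out | Follow-up runs from the last treatment (8.3), so a returner can be measured |
| Endpoints 2 to 5, subject does not return | No data | Out | Same result either way, because nothing is imputed |

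The disagreement is therefore about endpoints 2 to 5 for stoppers who return and, on the unlimited reading, about the safety summaries.

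**2. How large the effect could be.** From the documents: 5 listed sites × about 15 = 75 completers. Assumed: k replaced stoppers (1, 4 or 8), completers' mean discomfort 3 at the first session, stoppers scoring 6 or 8, and 60 of 75 completers satisfied. For satisfaction, all k stoppers return and either 40% or none of them are satisfied.

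- All treated: n = 75 + k.
- Mean discomfort = (75 × 3 + s × k)/n, where s is the stoppers' score. Under 7.2 it is 225/75 = 3.00.
- Share satisfied = (60 + q × k)/n, where q is the share of stoppers satisfied. Under 7.2 it is 60/75 = 80.0%.

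| k | n | Stopping (k/n) | Discomfort, s = 6 | Discomfort, s = 8 | Satisfied, q = 0.4 | Satisfied, q = 0 |
|---|---|---|---|---|---|---|
| 1 | 76 | 1.3% | 3.04 | 3.07 | 79.5% | 78.9% |
| 4 | 79 | 5.1% | 3.15 | 3.25 | 78.0% | 75.9% |
| 8 | 83 | 9.6% | 3.29 | 3.48 | 76.1% | 72.3% |

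For example, with k = 8 and s = 8, (225 + 64)/83 = 289/83 = 3.48.

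In general the shift is the share stopping times the difference between stoppers and completers. At 30% stopping and a 5-point discomfort difference it is 0.30 × 5 = 1.5 points. At 30% with no returning stopper satisfied it is 0.30 × 80 = 24 percentage points. The shift is zero if stoppers resemble completers, and the satisfaction shift is also zero if stoppers do not return.

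For adverse events, suppose 3 stoppers had an event and no completer did. Dropping them gives 0/75 (exact 95% interval 0 to 4.8%). Keeping them gives 3/78 = 3.8% (0.8% to 10.8%).

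**The case against.** The best defence is that 7.2 concerns recruitment, and that *evaluable* there means only counting toward the 15 completers. Section 14.1 is the dedicated place for analysis sets, and its treated-once rule would have little purpose if 7.2 overrode it. Discomfort is listed as a safety endpoint, so its natural home is the safety set. Section 9.4 has all adverse events recorded for each subject. This stands in large part. A reader might infer that the plan will drop stoppers' adverse events and discomfort scores. The documents do not establish that; they leave it possible. The defence does not settle the matter, because no sentence gives 14.1 precedence and the preceding sentence of 7.2 already covers replacement to reach 15 completers. An efficacy-only reading of 7.2 would still conflict with the performance set.

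The second defence is that the efficacy effect is narrow. It needs someone who stops early, returns and does worse, and no text requires visits after stopping. That is right, and it limits the reach to returners on endpoints 2 to 5. A reader might also infer that endpoint 1 contradicts 14.1. It need not, since an endpoint definition may narrow its own population.

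Third, section 8.2 limits discomfort at source through low starting energy, pausing and power reduction: "The procedure should NOT feel hot or intolerable to the patient". Pain can also be recorded as a graded adverse event (9.1, 9.2). Both make stopping for discomfort less likely or less invisible, but neither decides who is analysed.

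Finally, because 8.2 allows up to three sessions, it is not certain that one or two sessions count as non-completion. This is correct, and it is a further reason to define the term.

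**Conclusion.** The conflict is real and should be resolved before analysis. It is firm between 7.2 and the performance set. Between 7.2 and the safety set it is conditional on reading 7.2 without limit. If 7.2 is applied as worded, results on endpoints 2 to 5, and possibly the safety summaries, may look too favourable.

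The size is unknown. In the illustration, up to about 10% stopping moves mean discomfort by at most 0.48 points (3.48 − 3.00) and satisfaction by at most 7.7 percentage points (80.0 − 72.3). Every score, share and stopping count in it is assumed. The effect is zero if nobody stops early or if 14.1 governs.

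A reader might infer that the effect must be slight. That is plausible when few stop, but the documents give nothing that bounds it. A reader might equally infer that a success claim hangs on it. The plan sets no threshold for discomfort or satisfaction, so none would be crossed.

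**What to change.** 1. In 7.2, replace the disputed sentence with: *A subject who does not complete treatment may be replaced and does not count toward the 15 completers per site, but stays in every section 14.1 analysis set for which the subject qualifies.*
2. In 14.1, change Embrace to Evoke, and state that adverse events and discomfort are analysed in the safety set, including replaced subjects.
3. Define completion, for example as three treatments, and align the synopsis with 8.2.
4. Label endpoint 1 as a completer-only result.

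The cost is a few lines of text and slightly more tabulation; these changes call for no new data. The comfort and satisfaction figures may come out slightly less favourable. Two additions are optional and do not resolve the conflict. One is a discomfort table by session with a pre-set high-score cut. The other is endpoint 1 in the performance set, which would need extra blinded reads of non-completers' photographs.
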